## **Method**

### **Study Design and rationale of the reference standard: invasively measured**

#### **CBP**

This is a 12-month, prospective, randomized trial. The study is scheduled to commence in June 2018. We estimate to enroll a total of 252 patients with 84 subjects allocated into 3 arms. Details of the sample size calculation is provided in the statistics section.

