### **Study protocol**

Patients will be randomized to have hypertension management decisions made on the basis of the uAOBP, home BP, and central BP monitoring. Randomization will be done by using computer-generated randomization codes in 2 strata with baseline systolic BP (uAOBP) 130-155 mmHg and 155-180 mmHg. The BP measurements on left or right arm will also be determined by randomization codes.

To guide the management of hypertensive patients, medication adjustment will be made based on a published guideline with the measured BP through different BP monitoring methodologies. The use of different devices to obtain BP for guiding the care of hypertensive patients is aimed to determine whether these BP monitoring may be of comparable clinical value in routine practice. To achieve this, intervention patients will have medications titrated to normalize these different BP values. The target BP level, SBP 130 mmHg, of these different BP monitoring strategies are based on the latest guideline.

An overview of study protocol and acquired measures is presented in Table 1.

Although we encourage the adjustment of medication being adhered to the practice guideline, the choice of drug adjustment will be left to the discretion of the patient's attending doctor. During the measurement periods of home BP monitoring, no medication adjustment is allowable to preserve the comparability between different BP values. On the scheduled visits, the corresponding BP will be measured before meeting doctors and provided for clinicians to adjust patients' medication according to practice guideline. In summary, if the measured SBP is well within the target BP without possible side effects caused by antihypertensive agents, no medication adjustment is required. If the differences between measured SBP and target BP is less than 20 mmHg, the suggested maximal dose adjustment is 1 drug. If the BP differences are above 20 and 40 mmHg, addition of 2 drugs (or single pill combination) or 3 drugs (or single pill combination) are suggested, respectively. If low BP (less than 90/70mmHg) or any possible drug related side effects was noted, cautious adjustment of antihypertensive will be done. The dose adjustment and any possible side effects will be recorded throughout the whole study conduct period.

A sub-study will be performed to test the level of agreement between different measured BP values.

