#### **BP monitoring: uAOBP, central BP, and home BP**

Firstly, BP will be taken simultaneously from both upper arms by an oscillometric BP monitor (WatchBP Office Central; Microlife AG, Widnau, Switzerland). Subjects with SBP Differences between both arms more than 5 mmHg will be excluded. The performance of BP measurements will be adhered to the standard BP measurements procedures. For the uAOBP and CBP, the measurements will be conducted in a quiet room without the presence of clinical personnel. Patients will be seated in a quiet room without talking and taken as an average of 3 measurements with an automated device (HEM-907, Omron Healthcare, Lake Forest, IL) that has been preset to wait 5 minutes before measurements. Simultaneously, the central BP will be measured in the other upper arm. (WatchBP Office Central; Microlife AG, Widnau, Switzerland). The determination of the right or left upper arm for uAOBP or central BP will be made in a random order by computer generated random codes before the enrollment. As for the home BP measurements, a validated device (WatchBP Home; Microlife AG, Widnau, Switzerland) will be provided for all subjects allocated to the home BP arm to measure their BP at home. Subjects are requested to take BP in the morning (within 2 hours after awakening) and afternoon before meals for 7 consecutive days before the scheduled clinical visits. BP in the first day of the measurements will be discarded and an average of home BP (all BP reading and BP in the morning and in the afternoon) will be generated and provided

for clinicians to guide their treatment. The ambulatory BP of all subjects will be measured at baseline, at 3 months, and at the end of the study by a validated device (WatchBP O3 AFIB Ambulatory). Similarly, the choice of right or left arm for the measurement of ambulatory BP will be determined in a random manner. All the automated BP readings are stored digitally for analysis and corresponding BP values in each arm will be provided for clinicians to guide their hypertension management.

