### **Data Analysis and Statistical Analyses**

Based on data from our previous work, sample size (84 participants per group)

was determined on the basis of noninferiority between 3 independent groups ( $\alpha=0.05$ ;  $\beta=0.20$ ; standard deviation of ambulatory BP 11 mmHg; mean difference and non-inferior margin 5 mmHg, drop rate 10%).

We will test the normality of all parameters using the Shapiro–Wilk test. Categorical data are shown as proportions. Continuous data as means and standard deviations (SD) or as medium and interquartile ranges will be presented when appropriate.

Data will be analyzed on all patients who received the allocated strategy by intention-to-treat analysis if possible. For continuous variables of LV mass index, 24-hour ambulatory BP, heart rate, and quality of life, analysis will be undertaken using linear regression, with the dependent variable calculated as change over time. We will analyze DDD medication data recorded at all visits by using mixed regression models to account for repeated measures on individuals over time, with outcome variables log-transformed to correct heteroskedasticity where necessary.

The back-transformed means and confidence intervals are presented. Recommendations on medication use at each visit were categorized as maintain, increase, decrease or cease. A log-multinomial regression model will be used to assess the group differences for each of these 3 arms, with clustering on individuals to account for repeated measures over time.  $\chi^2$  test will be used to determine the

relationship between categorical variables. Intra-class correlations and paired t-test are used to assess the agreements between different strategies. A data safety monitoring board will be convened to oversee the progress of the study conduct and data relating to safety issue.

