### **Blood pressure threshold**

We adopt a common BP target based on the recommendation of the latest hypertension guideline for uAOBP and home BP. Usually, central BP is lower than brachial BP. However, central BP device can be further classified into two types according to whether there is a preserved BP amplification, ie. Devices purports to

give an estimate of central BP relative to measured brachial BP (type I) or purports to estimate the intra-arterial central BP (type II). We previously conducted a hypertension prevalence survey in the 2013–2016 National Nutrition and Health Survey in Taiwan. In this national representative cohort, a type 2 central BP device is adopted to measure central BP. As shown in this study, comparable values of central and brachial SBP/DBP were noted. We therefore decided to use the same BP target for central BP monitoring to guide hypertension treatment.

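### Agreement between BP methods is to be assessed only by paired t-test and intra-class correlation, neither of which states the within-patient difference in mmHg

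*Combined protocol and SAP*

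**What the plan says.** The Study protocol section promises an agreement sub-study in one sentence: "A sub-study will be performed to test the level of agreement between different measured BP values". It gives no size, estimand or acceptable difference. The only agreement methods named anywhere are in the Data Analysis and Statistical Analyses section: "Intra-class correlations and paired t-test are used to assess the agreements between different strategies". The form of the ICC is not stated, and limits of agreement and the SD of paired differences do not appear.

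Paired data will exist. Of the clinic session, the BP monitoring section says "Simultaneously, the central BP will be measured in the other upper arm", so uAOBP and central readings can be differenced within a patient. Table 1 lists uAOBP, home BP and central BP at Visits 1 to 7 with no restriction by arm. The BP monitoring section, however, says the home device "will be provided for all subjects allocated to the home BP arm to measure their BP at home". The number of pairs involving home BP is therefore unclear.

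One SBP target of 130 mmHg applies to all three methods. For central BP, the Blood pressure threshold section supports this by an earlier national survey in which "comparable values of central and brachial SBP/DBP were noted".

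**The concern.** Agreement between two BP methods is a question about individual patients: if one method reads a given value, how far away might the other read? A paired t-test does not ask this. It asks whether the average difference is zero, so wide scatter that cancels out passes unnoticed, while a small constant shift is flagged once there are enough pairs. The ICC does respond to scatter, but as a ratio to the spread between patients, so the same discrepancy in mmHg looks better in a varied sample than in a uniform one.

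The spread may well change during this trial. Patients enter in strata covering 130 to 180 mmHg and are then treated towards one target, so the ICC could shift between visits with no change in how closely the devices agree.

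What is at stake is how useful the sub-study is. The plan works in mmHg at patient level; for example, "If the differences between measured SBP and target BP is less than 20 mmHg, the suggested maximal dose adjustment is 1 drug". A reader of the sub-study will want the discrepancy on that scale, and the named methods do not supply it.

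**Working it through.** **The plan's own figure.** None is given for the agreement analysis. The only stated size is for the main trial: "We estimate to enroll a total of 252 patients with 84 subjects allocated into 3 arms". It reproduces. With SD 11, margin 5, a true difference of zero, 80% power and one-sided alpha 0.025 (the plan says 0.05 without giving sidedness), n = 2 × (1.96 + 0.84)² × 11² / 5² = 76 per group. For 10% dropout, 76 × 1.1 = 84 (76 / 0.9 gives 85). It is used below only for the number of pairs: up to 252 if every patient contributes, 84 if only one arm does.

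**Assumptions.** The documents give no SD of paired differences (s), so s = 5, 8, 10 and 12 mmHg are assumed. Differences are taken as normal, with one pair per patient and a two-sided 5% test.

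**1. Scatter that the t-test does not see.** Limits of agreement = bias ± 1.96 s. With zero bias:

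| s (mmHg) | 95% limits (mmHg) | patients differing by more than 10 mmHg | t-test non-significant |
|---|---|---|---|
| 5 | ±9.8 | 4.6% | 95% |
| 8 | ±15.7 | 21% | 95% |
| 10 | ±19.6 | 32% | 95% |
| 12 | ±23.5 | 40% | 95% |

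The last column is constant because the test is calibrated to the mean, whatever s is.

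**2. Small bias that the t-test flags.** The smallest significant observed bias is t(0.975, n−1) × s/√n. With s = 10:
- 252 pairs: 1.97 × 10/15.87 = 1.24 mmHg. An observed 1.2 mmHg falls just short (t = 1.2/0.630 = 1.905, p about 0.058).
- 84 pairs: 1.99 × 10/9.17 = 2.17 mmHg.

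The result therefore depends on the number of pairs. A true bias of 1 mmHg with s = 4 (limits −6.8 to 8.8) is significant with probability 62% at 84 pairs and 98% at 252.

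**3. ICC at a fixed discrepancy.** With zero bias, ICC = B²/(B² + s²/2), where B is the true between-patient SD. At s = 10, s²/2 = 50:
- B = 8: 64/114 = 0.56
- B = 11: 121/171 = 0.71
- B = 15: 225/275 = 0.82

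The limits are ±19.6 mmHg in all three. Using the observed SD of each method (S) instead, ICC = (S² − 50)/S². This gives 0.59 for S = 11 (the plan's ambulatory SD), and 0.74 and 0.85 for assumed S of 14 and 18. The pattern is the same.

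**4. Can the planned numbers support limits of agreement?** The approximate 95% CI half-width of each limit is 1.96 s √(1/n + 1.96²/(2(n−1))). At s = 10 this is 3.7 mmHg with 84 pairs and 2.1 mmHg with 252. With 76 or 228 (3 × 76) pairs it is 3.9 or 2.2 mmHg. No extra patients are needed.

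**The case against.** The strongest reply is that little depends on this analysis. Agreement is not among the primary or secondary outcomes in the Randomization, Outcomes, and Masking section. The sub-study has no decision rule, and the statistics sentence speaks of strategies without naming the sub-study. That link is an inference, although no other agreement method is offered. All of this stands, and it limits the point to a minor one.

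Second, the two statistics are named together. An absolute-agreement ICC penalises both bias and scatter, so it would often expose what the t-test misses; 0.56 hardly suggests good agreement. This stands in part. The form is not stated, and a consistency ICC would ignore a fixed bias. The same scatter also gives 0.82 in a more varied sample, and neither form gives a figure in mmHg.

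Third, the t-test is not useless. The 95% confidence interval of a Bland-Altman mean difference excludes zero exactly when the paired t-test gives p < 0.05. This stands: the need is to add the limits, not to discard the test. Readings are stored digitally and SDs are promised for continuous data, so limits could be derived later. The plan does not commit to doing so, nor to reporting the SD of the differences.

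A reader might also infer that the common 130 mmHg target is undermined. The documents do not support that. The target is already fixed from guidelines and, for central BP, the earlier survey. Changing the agreement statistic would alter neither how patients are managed nor the comparison of ambulatory SBP.

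**Conclusion.** The point holds as an inexpensive improvement to the agreement sub-study. The planned t-test and ICC do not state how far two methods may differ in one patient, and that quantity could be anywhere from ±9.8 to ±23.5 mmHg over assumed SDs of 5 to 12 mmHg without the t-test registering it. These sizes rest on assumed SDs and on normal, zero-bias differences; the true SD may lie outside the range.

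A reader might go further and infer that the sub-study will reach a wrong conclusion. The documents do not support this, because they nowhere say that a non-significant t-test, or any ICC value, will be taken as agreement. The defect is that the informative quantity is not pre-specified and the room for misreading is left open. The primary outcome and the sample size are not in question.

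**What to change.** In the Data Analysis and Statistical Analyses section, name the sub-study and specify the following:

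- **Main analysis:** Bland-Altman mean difference and 95% limits of agreement, each with 95% confidence intervals, for every pair of methods at the same visit.
- **Repeated visits:** a repeated-measures version if visits are pooled, because several pairs from one patient are not independent.
- **Proportional bias:** a check of whether the difference or its spread changes with the level of BP.
- **Supplementary:** an absolute-agreement ICC, with its form stated. The paired t-test may stay as a test of mean bias, with a statement that a non-significant result is not evidence of agreement.
- **Number of pairs:** state whether home BP pairs come from all patients or only the home BP arm, and reconcile the BP monitoring section with Table 1.

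The cost is a few sentences and a little programming on readings already planned. Recruitment, visits and the primary analysis do not change.

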### **Data Safety Monitoring**

We have established a Data Safety Monitoring Board (DSMB) to monitor all aspects of the study. All issues related to participants' safety will be reported by the Medical Safety Officer to the independent DSMB, which will monitor data and oversee participant safety and will meet twice a year to monitor safety. They will also advise the research steering committee the study progress and performance, and make recommendations regarding the study continuation and protocol change. Efforts to early identify any major adverse outcomes of therapy will be made by the DSMB. The following is the possible safety events relating to the intervention: Serum sodium  $\leq$ 132 or  $>$ 150 mEq/L; serum potassium  $<$ 3.0 or  $>$ 5.5 mEq/L; serum creatinine increase by at least 50% to a value  $\geq$ 1.5 mg/dL since the last study lab; heart rate  $<$ 40; ECG complete heart block, or bradycardia  $<$ 40 beats/min; injurious falls; syncope; any unexpected events for which the investigator believes that could be attributed to the intervention strategies. Serious adverse events are any adverse events that meet any of the following criteria: fatal or life-threatening, result in

significant or persistent disability, require or prolong hospitalization, and any events that investigators judge to represent significant hazards or harm to research.

## **Discussion**

### **Rationale**

The BP measurement is the clinical procedure of greatest importance given it serves as an imperative foundation in the management of hypertension, which is the most significant cardiovascular risk factor across the globe. However, a substantial whitecoat effect, the difference between office and out-of-office BP, can be observed in the measurement process of office BP in routine clinical practice, which can make the adjustment of antihypertensive agents a challenging task. Subsequently, home BP and uAOBP have been confirmed as successful strategies to eliminate the whitecoat effects. In addition, central BP has been shown to better conventional office BP in the prediction of cardiovascular risk and may be a more cost-effective strategy in the diagnosis of hypertension. In the era of evidence-based medicine, clinical trials are required to investigate the comparative effectiveness between these readily available BP monitoring strategies to inform clinical practice decisions. Using the gold standard of BP monitoring, the ambulatory BP, as the primary endpoint, we suggest home BP monitoring may be non-inferior to uAOBP and central BP monitoring as a guiding tool in the management of hypertension. Home BP is obtained by consecutive measurements and therefore is associated with a better accuracy and prognostic value than

conventional office BP. Moreover, home BP monitoring can be conducted in an easier way than uAOBP. If a comparable effectiveness could be demonstrated, it may have the potential to become the standard guiding procedure for hypertension.

**Challenges in using office BP values to guide the clinical management of hypertension**

Using conventional office BP in the management of hypertension is heavily influenced by the busy and hurry clinical environment. In a previous review article, it has been demonstrated that the routine office BP is substantially higher than research office BP, uAOBP, and daytime ambulatory BP. Therefore, it could be risky and imprudent to titrate antihypertensive agents solely based on routine office BP. As such, many alternative strategies have been proposed to replace conventional office BP to guide the management of hypertension. With the corresponding feasibility and effectiveness, home BP might be the strategy of choice to be implemented in the care of hypertensive subjects. However, its comparative effectiveness and safety in comparison with uAOBP and central BP monitoring have never been evaluated.

**uAOBP: the best BP measuring technique?**

Unattended AOBP, with its potential to eliminate whitecoat effect, has been adopted in SPRINT study. One may partly attribute the success of SPRINT study to

the use of a more accurate BP measurement technique. It is therefore a promising technique to be used in routine clinical practice. However, in the practice of some clinical settings, it is probably unrealistic to implement this technique given its requirement of time, space, and the investment in the device cost. Without a randomized control trial comparing the effectiveness and safety between different BP monitoring strategies, it is difficult to make an evidence-based decision to guide the clinical management of hypertension.

### **Double blind versus open label design for the treatment strategies**

We designed this study as a double-blind study for the clinical information will be provided for clinicians without the knowledge of the BP monitoring used for measure subjects' BP. The allocation concealment and blinding to patients, care givers, and outcome assessors will be rigorously kept avoiding possible placebo or performance bias. To our knowledge, it may be the first randomized controlled trial using the double-blind technique to evaluate the best BP monitoring strategy.

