#### **Study Population**

Patients with hypertension will be recruited via outpatient clinics and advertisement and in our hospital. Inclusion criteria are as follows: 20 to 90 years of age; nonpregnant; receiving antihypertensive therapy for uncomplicated essential hypertension and taking  $\geq 1$  but  $\leq 2$  types antihypertensive drugs (to rule out complicated or resistant hypertension) or hypertension newly diagnosed by uAOBP ( $uAOBP > 130$  mmHg at screening visit). Exclusion criteria are as follows: Poor adherence to medication; unable to conduct self-measurement blood pressure; history of polycystic kidney disease; congestive heart failure (a recent assessment of left ventricular ejection fraction  $< 40\%$  prior to screening visit); chronic kidney disease with estimated glomerular filtration rate  $< 30$  mL/min/1.73m^2 (MDRD) at screening visit; a recent document of severely abnormal LV mass index ( $> 59$  g/m2.7

in women and >64 g/m^2.7 in men) prior to screening visit; secondary causes of hypertension; uncontrolled hypertension (uAOBP >180/100 mm Hg at screening visit); history of severe aortic valve disease; history of upper limb obstructive atherosclerosis; BP Differences more than 5 mmHg between both arms at screening visit.

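### The patient-blinding claim is not supported for the two home BP contrasts if, as the BP monitoring section says, the monitor goes to the home BP arm; Table 1 suggests otherwise and the two are not reconciled

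*Combined protocol and SAP*

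**What the plan says.** The Abstract (Methods and analysis) states that patients as well as physicians are blinded to allocation, by means of a standardized report of the BP values. The Discussion section on double-blind versus open-label design goes further: "The allocation concealment and blinding to patients, care givers, and outcome assessors will be rigorously kept avoiding possible placebo or performance bias". It adds that this may be the first randomized trial to use the double-blind technique for this question. The section on randomization, outcomes and masking describes how physicians are masked: the report form does not reveal the device. For participants, that section claims only blinding to outcome variables, and it exempts patient-reported outcomes and adverse events.

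The section on BP monitoring says that a validated home device "will be provided for all subjects allocated to the home BP arm to measure their BP at home", with morning and afternoon readings on 7 consecutive days before scheduled visits. For the clinic methods, uAOBP is taken in one arm and "Simultaneously, the central BP will be measured in the other upper arm".

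Other text carries no restriction by arm:

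- Table 1 ticks Home BP at Visits 1 to 7, including the randomization visit, and has no arm column.
- Study Population excludes any patient "unable to conduct self-measurement blood pressure".
- Study protocol states: "During the measurement periods of home BP monitoring, no medication adjustment is allowable to preserve the comparability between different BP values". It also plans an agreement study: "A sub-study will be performed to test the level of agreement between different measured BP values".
- The secondary outcomes include change in home BP.

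**The concern.** A patient is masked only if the experience of the trial does not reveal the arm. A report handed to a clinician does nothing for that. A week of self-measurement before each visit, with a device issued because of the allocation, is visible to the patient.

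The Introduction hypothesizes that home BP-guided care is non-inferior to uAOBP-guided and to central BP-guided care. The contrasts with doubtful patient masking are therefore exactly those the trial is meant to test. Patients who know their arm may behave or report differently. The outcomes most exposed are quality of life and side effects. Treatment may also be touched if the patient's knowledge reaches the clinician, because "the choice of drug adjustment will be left to the discretion" of the attending doctor. A reader who relies on the Discussion would take the home contrasts as double-blind and free of performance bias when the documents do not establish this.

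**Working it through.** **1. Plan's own figures.** The design section gives 252 patients in three arms and the allocation is 1:1:1, so 252 / 3 = 84 per arm. This matches the 84 per group in the statistics section. Patients outside the home arm: 252 − 84 = 168. These are enrolled numbers, before the planned 10% dropout.

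**2. What could mask a patient.** The Abstract, the masking section and the Discussion describe one device for masking patients and physicians: the standardized report. It is addressed to clinicians. No section describes sham or parallel home measurement in the clinic arms. For uAOBP versus central BP, simultaneous measurement in opposite arms does the job: both groups go through the same procedure and cannot tell which value guides care.

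**3. The two readings, by contrast.** Three arms give 3 × 2 / 2 = 3 pairwise contrasts, of which 2 involve home BP.

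| Contrast | Only the home arm self-measures | All arms self-measure |
|---|---|---|
| Home vs uAOBP | not patient-masked | can be masked |
| Home vs central | not patient-masked | can be masked |
| uAOBP vs central | can be masked | can be masked |
| Not patient-masked | 2 of 3 | 0 of 3 |

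On the first reading, 84 patients can infer that they are in the home arm and 168 that they are not. Both statements need the assumption that patients know of the three strategies. A patient given a monitor learns the arm only by knowing that others get none.

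**4. How far the other text goes toward all-arm self-measurement.**

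- *Table 1, Visit 1.* This is the strongest item. If the tick is a measurement, as the uAOBP and central BP ticks in that column appear to be, the 7 days of readings precede randomization and so involve everyone. The tick could also mean device issue.
- *Change in home BP as an outcome.* A change needs a baseline value, which again points to readings before allocation. The outcome could still be intended for the home arm alone.
- *Exclusion for inability to self-measure.* This would be needed on either reading, since anyone may be allocated to the home arm.
- *Bar on medication changes during home measurement, and the agreement study.* Neither names an arm. The home arm alone could supply paired values for the intra-class correlations and paired t-tests.

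Together these make all-arm self-measurement plausible. None of them supplies a device to the other two arms, and the one sentence that does supply a device names the home arm.

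**5. Size of any bias.** Nothing in the documents gives the effect of a patient's knowledge of the arm on 24-hour SBP, quality of life or reported side effects. No figure is offered.

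**The case against.** The best defence is that every arm self-measures. Table 1, the exclusion criterion, the bar on medication changes and the outcome list all omit any restriction by arm, and the sentence on the home device does not say that only the home arm receives one. This carries real weight. It means the documents do not show that patient blinding must fail. It does not remove the conflict, because on that reading the BP monitoring section leaves out the devices for 168 patients.

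A second defence is that the primary outcome is recorded automatically and LV mass is read by a technician blinded to allocation. That is correct, and outcome assessment of these two measures is not in question. The Discussion, however, also claims that performance bias is avoided, and objective recording does not secure that. Against this, an adherence effect of self-monitoring may fairly be regarded as part of the home strategy and not as bias.

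A reader might also infer that physicians are unblinded, because "an average of home BP (all BP reading and BP in the morning and in the afternoon) will be generated and provided" to them. The documents do not support that as a finding. The masking section states an explicit mechanism for physicians, and the parenthesis can mean one average over all readings. Only if separate morning and afternoon averages appear on the form would its content reveal the home arm. What the report shows is not stated, so this is a request for clarification.

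**Conclusion.** The point holds as an internal inconsistency: a stated property, patient blinding, is not supported by the procedure as written. If only the home arm self-measures, and patients know of the three strategies, 2 of 3 contrasts are not patient-masked. Those two are the contrasts in the non-inferiority hypothesis; uAOBP versus central BP can be masked. If all arms self-measure, no contrast need be unmasked for patients, and the defect is an incomplete BP monitoring section. Either way, text has to change.

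It would be tempting to conclude that the trial is open-label or that its primary result is biased. Neither follows. The documents leave open who self-measures, the ambulatory endpoint is device-recorded, and neither the size nor the direction of any bias can be derived. The consequence is for how the home contrasts may be described and interpreted, most of all for quality of life and side effects.

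**What to change.** 1. Reconcile the BP monitoring section with Table 1: state which arms measure home BP and from which visit, and whether the Visit 1 tick is a measurement.
2. If only the home arm self-measures, limit the patient-blinding statement in the Abstract, and the patient-blinding, performance-bias and first-double-blind statements in the Discussion, to uAOBP versus central BP. Interpret the two home contrasts as not patient-masked, particularly for quality of life and side effects.
3. If all arms self-measure, say so in the BP monitoring section, including that the other two arms receive a device, and keep the patient-blinding claim.
4. As a minor clarification, state whether the clinician report has the same content in all arms.

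These are changes of wording. No endpoint, analysis or sample size changes. The cost, if only the home arm self-measures, is a narrower blinding claim and a narrower claim to be the first double-blind trial of its kind.
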